6.4.1.4. Adverse Event of Special Interest

An adverse event of special interest (AESI) is defined as an AE of scientific and medical interest specific to the understanding of the study drug and requiring close monitoring and rapid communication by the Investigator to the Sponsor. An AESI may be serious or non-serious. The rapid reporting of AESIs allows ongoing analysis of these events in order to characterize and understand them in association with the use of the study drug.

Treatments with immunosuppressants, including rilonacept, may result in an increase in the risk of malignancies. Therefore, malignancy is an AESI for rilonacept. Any AE of malignancy (excluding basal cell carcinoma of the skin) requires reporting to the [REDACTED] Pharmacovigilance (PHV) within 24 hours after the time the site personnel first learn about the event, following the process as described in Section 6.4.6.

6.4.1.5. Adverse Reaction

Any noxious and unintended response to the study drug (i.e., where a causal relationship between the study drug and an AE is at least a reasonable possibility) related to any dose should be considered adverse drug reaction.

6.4.1.6. Suspected Unexpected Serious Adverse Reaction

Suspected Unexpected Serious Adverse Reaction (SUSAR) is an adverse reaction that is “unexpected”, i.e., it is not listed (or not listed at the severity that has been observed) in the designated Reference Safety Information of the Investigator’s Brochure. Evaluation and reporting requirements for SUSARs are detailed in Section 6.4.8.

6.4.2. Assessing Adverse Events

6.4.2.1. Relationship to Study Drug

The Investigator’s assessment of an AE’s relationship to the study drug is part of the documentation process, but it is not a factor in determining what is or is not reported in the study. If there is any doubt as to whether a clinical observation is an AE, the event should be reported.

The relationship or association of the study drug in causing or contributing to the AE will be characterized by Investigator using the following classification and criteria:

- **Not Related:** when the AE is definitely caused by the subject’s clinical state or the study procedure/conditions
- **Unlikely Related:** when the temporal association between the AE and the study drug is such that the drug is not likely to have any reasonable association with the AE
- **Possibly Related:** when the AE follows a reasonable temporal sequence from the time of study drug administration but could have been produced by the subject’s clinical state or the study procedures/conditions

- **Related:** when the AE follows a reasonable temporal sequence from administration of the study drug, abates upon discontinuation of the drug, follows a known or hypothesized cause-effect relationship, and (if appropriate) reappears when the drug is reintroduced

6.4.2.2. Intensity

The severity of an AE will be recorded as one of the following:

- **Mild:** easily tolerated, does not interfere with normal daily activities, does not require intervention
- **Moderate:** causes some interference with daily activities; minimal, local, or noninvasive intervention indicated
- **Severe:** as a consequence of the event, daily activities are limited or completely halted; hospitalization or prolongation of hospitalization indicated

Changes in the severity of an AE should be documented to allow an assessment of the duration of the event at each level of intensity to be performed. Adverse events characterized as intermittent do not require documentation of onset and duration of each episode.

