1.3.1. Safety of Rilonacept

For a detailed review of the available rilonacept safety data, please refer to the current Investigator Brochure and the ARCALYST[®] package insert located in the Pharmacy Manual. Rilonacept has been evaluated in 23 studies, including 22 complete and 1 ongoing. In the completed studies, 2243 subjects (2152 patients and 91 healthy volunteers) were exposed to rilonacept. Thirty of these patients were pediatric (<18 years of age). Doses up to 320 mg subcutaneously (SC) once weekly and 2000 mg intravenously (IV) monthly have been studied for different indications, including CAPS, gout, and other inflammatory disorders.

Injection Site Reactions

In clinical studies with rilonacept, the most common and consistently reported AE associated with rilonacept was injection site reaction (ISR). The ISRs included erythema, swelling, pruritus, mass, bruising, inflammation, pain, edema, dermatitis, discomfort, urticaria, vesicles, warmth, and hemorrhage. Most ISRs were mild to moderate. In the gout clinical studies, approximately 1% of subjects treated with rilonacept discontinued due to ISRs. Similar results have been seen in other patient populations.

Infections

Interleukin-1 blockade may interfere with immune response to infections. Serious life-threatening infections have been reported in clinical trials in subjects treated with rilonacept.

Changes in Laboratory Parameters

Cholesterol and lipid levels may be reduced in patients with chronic inflammation. Subjects treated with rilonacept in clinical trials experienced increases in their mean total cholesterol, high-density lipoprotein (HDL) cholesterol, low-density lipoprotein (LDL) cholesterol, and triglycerides.

Immunogenicity

As with all therapeutic proteins, there is a potential for immunogenicity. Antibodies directed against the receptor domains of rilonacept were detected using an enzyme-linked immunosorbent assay (ELISA). In clinical trials with rilonacept, approximately 30% to 35% of subjects tested positive for treatment-emergent antibodies to rilonacept on at least 1 occasion.

Systemic Hypersensitivity Reactions

Hypersensitivity reactions are a potential risk with protein therapeutics in general. In clinical studies with rilonacept, systemic hypersensitivity reactions have been rare.

Malignancies

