6.4.1.2. Treatment-emergent Adverse Event

A treatment-emergent AE (TEAE) is defined as any event not present before exposure to the study drug or any event already present that worsens in either intensity or frequency after exposure to the study drug.

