6.4.3. Recording Adverse Events

Each subject should be monitored for the development of any AEs. This information should be collected by asking nonleading questions (such as “How are you feeling?”) and from observations of and conversations with patients. AEs may also be collected by direct physical exam, diagnostic procedures, or any other appropriate source.

At every study visit (telephone or at the site), subjects will be asked a standard nonleading question to elicit any medically related changes in their well-being. They will also be asked if they have been admitted to the hospital, had any accidents, used any new medications, or changed concomitant medication regimens (both prescription and over-the-counter medications).

All AEs (serious and non-serious) will be documented in the subject’s source documents and recorded in the eCRF. Any clinically relevant (as determined by the Investigator) deterioration in laboratory assessments or other clinical findings is considered an AE and must be recorded in the subject’s source documents and in the eCRF.

The AE term should be reported in standard medical terminology when possible. Also, when possible, signs and symptoms indicating a common underlying pathology should be noted as one comprehensive event. Information to be collected includes the following:

- Event term
- Date and time of onset
- Investigator-specified assessment of severity and relationship study drug
- Date of resolution of the event

- Seriousness
- Any required treatment or actions
- Outcome
- Whether or not it caused the subject to discontinue the study drug.
- Whether or not the AE is an Injection Site Reaction (ISR). ISR is defined as any AE that occurs at the study drug injection site. If an ISR is observed, the subject may be treated at the discretion of the Investigator.

Adverse events resulting from concurrent illnesses, reactions to concurrent illnesses, reactions to concurrent medications, or progression of disease states must also be reported. All AEs will be followed to adequate resolution. The Medical Dictionary for Regulatory Activities (MedDRA) will be used to code all AEs.

Any medical condition that is present at the time that the subject is screened but does not deteriorate should not be reported as an AE. However, if the condition deteriorates at any time during the study, it should be recorded as an AE.

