7.7.8. Safety Analyses

Treatment-emergent AEs (TEAEs), defined as AEs that start or increase in severity after the first dose of study drug and before 6 weeks after the last dose of study drug, will be coded to system organ class and preferred term using the most recent version of MedDRA. TEAEs will be analyzed for all subjects combined and by treatment group in the RW period. Further analyses by severity and relationship to study drug as well as analyses of serious TEAEs will be presented.

Descriptive statistics will be used to summarize safety endpoints by visit for all subjects combined in the RI period and by treatment group in the RW period. Two-sided 95% CIs will be presented where meaningful. Data summaries will be displayed for clinical laboratory analyses (including safety laboratory measurements, ADAs, etc.), vital signs measurements, ECGs, and physical examination findings.

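### The intermittent-event rule lets an injection site reaction that began in the run-in go undated in the randomized withdrawal period, and the TEAE definition does not say where it is then counted

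*Protocol*

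**What the plan says.** Section numbers refer to protocol version 3.0 unless stated.

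- **Recording rule (6.4.2.2).** "Adverse events characterized as intermittent do not require documentation of onset and duration of each episode". No type of AE is excepted. The same section keeps one safeguard: "Changes in the severity of an AE should be documented".
- **AE fields (6.4.3).** Each AE record carries "Date and time of onset", a resolution date and a yes/no flag for ISR. Nothing says that ISRs are intermittent, and nothing says that each one is a separate AE.
- **TEAE, AE section (6.4.1.2).** A TEAE is a new event, or "any event already present that worsens in either intensity or frequency after exposure to the study drug".
- **TEAE, analysis section (7.7.8).** TEAEs are "defined as AEs that start or increase in severity after the first dose of study drug", up to 6 weeks after the last dose. They are summarized for all subjects combined and by treatment group in the RW period. Frequency is not mentioned, and no rule is given for an AE that began in the run-in.
- **Exposure (3.1.2, 7.5).** All subjects receive rilonacept weekly for 12 weeks before randomization, and the safety set is defined by a run-in dose.
- **Expected harm (1.3.1).** ISR is named as the most common AE of rilonacept.

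**The concern.** In a randomized withdrawal design, both arms reach randomization already exposed to the drug and possibly already carrying an open AE record. A comparison of AEs after randomization needs to know which events occurred after the first blinded RW dose. For a reaction that comes and goes with weekly injections, that information lies in the episode dates, and the protocol waives exactly those for any AE the investigator calls intermittent.

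At stake is the trial's only randomized, placebo-controlled comparison of the drug's most common AE. The primary efficacy result is not touched.

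An SAP could choose how to assign events to periods. It could not recover RW episode dates that the protocol told sites they need not collect.

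**Working it through.** The plan gives no figure on this point, so there is none to reproduce. The check sets the passages side by side and then illustrates size under stated assumptions.

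**Step 1. Can an ISR plausibly be recorded as intermittent?** Dosing is every 7 ± 2 days (5.2). The label appended to version 2.0 says most ISRs last one to two days (its section 6.2). A subject who reacts repeatedly therefore has short reactions with gaps between them. The protocol permits recording these as separate AEs or as one intermittent AE.

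**Step 2. What happens to a run-in ISR that recurs in RW?**

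| How it is recorded | Assigned to RW by start date (or by a severity increase in RW) | First-dose anchor of 7.7.8 applied literally |
|---|---|---|
| Separate AE per reaction | RW reactions counted | Run-in reactions are TEAEs too and may be shown under the randomized arm |
| One intermittent AE, severity rises in RW | Rise is documented, so counted | TEAE, may be shown under the randomized arm |
| One intermittent AE, severity unchanged | Not counted in RW | TEAE, may be shown under the randomized arm whether or not it recurred after randomization |

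The gap is in the last row for assignment by start date, and in all three rows for the literal anchor. Under the literal anchor, a reaction to run-in rilonacept can be listed under placebo. Section 7.5 says safety analyses follow the treatment actually received, but it does not say how period and treatment are matched for an AE that spans randomization.

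**Step 3. Do the two TEAE definitions agree?** No. Section 6.4.1.2 counts worsening in intensity or frequency; 7.7.8 counts severity only. An ISR that becomes more frequent in RW at the same severity meets the first and not the second, and its frequency cannot be judged without episode dates.

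**Step 4. Illustration of size.**
- ISR rates: 48% rilonacept, 13% placebo (label Table 1, Part A, version 2.0 appendix). These come from treatment-naive CAPS patients over six weeks and are used only as a scale.
- *s*: share of RW ISR subjects whose reaction sits in one intermittent record with a run-in start and unchanged severity. The documents give no value; 0 to 0.75 is assumed, equal in both arms.
- Formula, for assignment by start date: reported rate = true rate × (1 − *s*).

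| *s* | Rilonacept | Placebo | Difference |
|---|---|---|---|
| 0 | 48% | 13% | 35 points |
| 0.25 | 48 × 0.75 = 36% | 13 × 0.75 = 9.75% | 26.25 |
| 0.50 | 48 × 0.50 = 24% | 13 × 0.50 = 6.5% | 17.5 |
| 0.75 | 48 × 0.25 = 12% | 13 × 0.25 = 3.25% | 8.75 |

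With equal loss the ratio of the two rates is unchanged (48/13 = 3.7 throughout); the difference shrinks in proportion.

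**The case against.** The strongest reply is that the consequence is not written in the protocol. ISRs are never designated intermittent. A reaction that resolves in a day or two, followed a week later by another at a rotated site, fits separate AEs with separate onset dates. Section 7.7.8 does not say that RW assignment is by start date, and 7.7 leaves data conventions to the SAP, which is not shown. Each record still has overall onset and resolution dates, so an SAP could tabulate AEs present during RW without episode dates. Severity increases are captured. ISRs are mostly mild to moderate (1.3.1), and the label already has a placebo-controlled estimate.

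All of this stands, and it limits both certainty and size. It does not remove the point. A record left open across randomization shows that the AE was not closed, not that a reaction followed an RW injection. Counting every overlapping record could credit placebo with reactions that occurred only on run-in rilonacept. The missing dates are a matter of data capture, which an analysis plan cannot repair.

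Two stronger readings are tempting:

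- A reader might infer that run-in ISRs necessarily drop out of the RW comparison. The documents do not say so: it takes an intermittent label, unchanged severity and assignment by start date together.
- A reader might infer that rilonacept could look no worse than placebo, since 75% loss gives 12% against 13%. That holds only if the loss falls on rilonacept alone. The rule covers both arms, both had run-in injections, and nothing in the documents supports a one-sided share.

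**Conclusion.** The protocol permits a recording practice under which an ISR recurring after randomization has no RW date, and pairs it with a TEAE definition anchored before randomization. Depending on the convention adopted, unchanged recurrences can be missed in RW, or run-in reactions can be shown under the randomized arm, including placebo. The two TEAE definitions also disagree on frequency.

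This is a conditional risk of unknown size, possibly zero. If it occurs with assignment by start date and equal loss in both arms, the difference between arms is understated in proportion to the share lost. Those figures rest on label rates from another population and an assumed share. The literal first-dose anchor would misplace events instead, by an amount the documents do not allow one to estimate. The wording should be changed because the remedy is small and the information cannot be recovered later.

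**What to change.** 1. **Sections 6.4.2.2 and 6.4.3:** exempt ISR-flagged AEs in the RW period from the intermittent-event rule. At minimum, require a new AE record with its own onset date for the first ISR after the first RW dose.
2. **Section 7.7.8:** define RW treatment-emergence from the first RW dose. Count an RW ISR as any ISR occurring after that dose and before bailout rilonacept, whether or not the subject had an ISR in the run-in.
3. **Sections 6.4.1.2 and 7.7.8:** reconcile the TEAE definitions so that both treat frequency the same way.

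Cost: a few more AE entries per subject during RW under the minimum option. Recording every RW reaction would cost more, because dosing is weekly and the period is event-driven. The ISR flag and onset field already exist (6.4.3), and the diary already records every dose (5.8), so no visit or form is added. Treatment and clinical management are unaffected.

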6.4.3. Recording Adverse Events

Each subject should be monitored for the development of any AEs. This information should be collected by asking nonleading questions (such as “How are you feeling?”) and from observations of and conversations with patients. AEs may also be collected by direct physical exam, diagnostic procedures, or any other appropriate source.

At every study visit (telephone or at the site), subjects will be asked a standard nonleading question to elicit any medically related changes in their well-being. They will also be asked if they have been admitted to the hospital, had any accidents, used any new medications, or changed concomitant medication regimens (both prescription and over-the-counter medications).

All AEs (serious and non-serious) will be documented in the subject’s source documents and recorded in the eCRF. Any clinically relevant (as determined by the Investigator) deterioration in laboratory assessments or other clinical findings is considered an AE and must be recorded in the subject’s source documents and in the eCRF.

The AE term should be reported in standard medical terminology when possible. Also, when possible, signs and symptoms indicating a common underlying pathology should be noted as one comprehensive event. Information to be collected includes the following:

- Event term
- Date and time of onset
- Investigator-specified assessment of severity and relationship study drug
- Date of resolution of the event

- Seriousness
- Any required treatment or actions
- Outcome
- Whether or not it caused the subject to discontinue the study drug.
- Whether or not the AE is an Injection Site Reaction (ISR). ISR is defined as any AE that occurs at the study drug injection site. If an ISR is observed, the subject may be treated at the discretion of the Investigator.

Adverse events resulting from concurrent illnesses, reactions to concurrent illnesses, reactions to concurrent medications, or progression of disease states must also be reported. All AEs will be followed to adequate resolution. The Medical Dictionary for Regulatory Activities (MedDRA) will be used to code all AEs.

Any medical condition that is present at the time that the subject is screened but does not deteriorate should not be reported as an AE. However, if the condition deteriorates at any time during the study, it should be recorded as an AE.

6.4.3.1. Adverse Events Based on Signs and Symptoms

All AEs spontaneously reported by the subject or reported in response to the open question from the study personnel or revealed by observation will be collected and recorded in the eCRF. When collecting AEs, the recording of a diagnosis is preferred (when possible) to the recording of a list of signs and symptoms. However, if a diagnosis is known and there are other signs or symptoms that are not generally part of the diagnosis, the diagnosis and each sign or symptom will be recorded separately.

6.4.3.2. Adverse Events Based on Examinations and Tests

If an abnormal laboratory value/vital sign is associated with clinical signs and symptoms, the sign or symptom will be reported as an AE and the associated laboratory result/vital sign will be considered as additional information. Wherever possible the reporting Investigator uses the clinical rather than the laboratory term (e.g., anemia vs low hemoglobin value). In the absence of clinical signs or symptoms, clinically significant findings on examinations and tests should be reported as AEs.

Any new or aggravated clinically significant abnormal medical finding at a physical examination as compared with the baseline assessment will be reported as an AE.

6.4.3.3. Pericarditis Disease-related Events

Signs, symptoms, and abnormal findings associated with pericarditis are to be captured as a pericarditis recurrence event rather than as an AE unless the event is more severe than expected for the subject. In any case, pericarditis recurrence is required to be captured in the eCRF (see Section [6.2.3](#)) within 24 hours of learning of the event.

6.4.4. Time Period for Collection of Adverse Events

Adverse events will be assessed from the time the subject's signs the ICF and through 6 weeks after the last dose of study drug.

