 - c. Permanently sterile following documented hysterectomy, bilateral salpingectomy, bilateral oophorectomy, or bilateral tubal ligation or having a male partner with vasectomy as affirmed by the subject OR
 - d. If of childbearing potential, must agree to use a highly effective method of contraception during the study and for 3 months after the last study drug administration (e.g., hormonal contraceptives associated with inhibition of ovulation, intrauterine device [IUD], intrauterine hormone-releasing system [IUS], or sexual abstinence)
9. If male and sexually active, must have documented vasectomy or must practice birth control and not donate sperm during the study and for 3 months after the last study drug administration.
10. Must be up-to-date with all immunizations, in agreement with current local immunization guidelines for immunosuppressed subjects, before RI baseline (first administration of study drug).
11. Is able to adequately maintain a daily subject diary according to protocol.
12. Must be able to adhere to the study visit schedule and understand and comply with the other protocol requirements.
13. Agrees to refrain from making any new, major lifestyle changes that may affect pericarditis symptoms (e.g., changing exercise pattern) from the time of the ICF is signed through the end of the double-blind RW period.

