4.3. Subject Completion, Withdrawal from Study, and Study Drug Discontinuation

4.3.1. Completion

A subject will be considered to have completed the study if she/he has completed the RW period and has completed assessments at the EORW visit. At the EORW visit all subjects who are still receiving study treatment (blinded therapy or open-label bailout) will be offered an opportunity to receive up to an additional 24 months of open-label rilonacept treatment based on their clinical status and at the discretion of the investigator, and after signing the LTE informed consent.

Additionally, after the randomized withdrawal period has been closed when at least 22 confirmed recurrent pericarditis events have been accrued, subjects who have not yet completed the full 12 weeks of RI period at that time will be allowed to continue tapering of concomitant meds in the RI period; those subjects who achieved clinical response by Week 12 will be given the option to receive open-label rilonacept in the LTE without having to proceed through the RW period.

Any subject who in the opinion of the Investigator should not continue open-label rilonacept in LTE will be withdrawn from the study.

Subjects who elect not to enter the LTE will be followed for 6 weeks (safety follow up) after receiving the last study drug administration.

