5.6.5. Prohibited Concomitant Medicines During the Study

The following concomitant medications are prohibited throughout the duration of the study including the LTE:

- Interleukin-1 (IL-1) blockers other than rilonacept
- IL-6 blockers
- Janus-activating kinase inhibitors
- TNF inhibitors
- Potent immunosuppressants (azathioprine, mycophenolate mofetil, cyclosporine, tacrolimus, sirolimus, mercaptopurine, cyclophosphamide, chlorambucil, nitrogen mustard, or other alkylating agents, agents that deplete B or T cells [e.g., rituximab, alemtuzumab])
- Live (attenuated) vaccines, which are prohibited during the study and within 12 weeks after the last study drug administration

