6.1.8. Safety Follow-up Visit

The SFU visit is to be conducted 6 weeks after the last dose of study drug. In the event that a subject permanently discontinues study drug but does not withdraw the informed consent, the Investigator should continue to follow the subject per protocol for the remainder of that study period. Refer to Section 13.1 for a comprehensive list of procedures in the Schedule of Activities for this visit.

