6.3. Safety Assessments

Safety assessments to be performed at study visits are summarized in Section 13.1 and include: assessment of AEs (Section 6.4), physical examinations (full and abbreviated) including vital signs measurements, chest x-ray, TB screening, and clinical laboratory tests (serology, hematology, chemistry, urinalysis) (Section 6.6). A pregnancy test (Section 6.6.6) will be conducted at screening and as needed during the study and must be performed 6 weeks after the last study drug administration.

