6.4.7. Pregnancy

Pregnancy is regarded as an AE only if there is a suspicion that study drug may have interfered with the effectiveness of a contraceptive medication. Nonetheless, any pregnancy that occurs during study participation (including pregnancy in a female partner of a male subject) must be reported to the [REDACTED] PHV in the same way and using the same procedures as for an SAE (Section 6.4.6). The subject with pregnancy must not receive (additional) study drug. The pregnancy must be followed up to determine outcome (including spontaneous miscarriage, elective termination, normal birth, or congenital abnormality) and status of mother and child, even if the subject was discontinued from the study. Pregnancy complications and elective terminations for medical reasons must be reported as an AE or SAE. Spontaneous miscarriage must be reported as an SAE.

Any SAE occurring in association with a pregnancy, brought to the Investigator's attention after the subject has completed the study, and considered by the Investigator as possibly related to the study drug, must be promptly reported to the [REDACTED] PHV.

In the event that a subject is found to be pregnant after having received at least 1 study drug dose, the study drug must be discontinued, and the pregnancy will be followed to term and the status of mother and child will be reported to the [REDACTED] PHV after delivery. Instances of perinatal death or congenital abnormality, if brought to the attention of the Investigator at any time after cessation of study drug, will be reported to the [REDACTED] PHV within 24 hours.

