6.6.6. Pregnancy Test

For women of child-bearing potential, a urine pregnancy test using a licensed test (dipstick) should be performed prior to receiving the first administration of study drug and as needed during the study. When needed, serum pregnancy test should be performed. The purpose of pregnancy test is to prevent embryo/fetal exposure to study drug. Subjects with positive or indeterminate pregnancy test during the screening are not eligible for the study.

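### For subjects who leave the study at the 6-week safety visit, about half of the protocol's 3-month conception period and 12-week live-vaccine period has no scheduled contact, and an uncomplicated pregnancy conceived in that gap need not be reported

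*Protocol*

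**What the plan says.** **Restrictions after the last dose.** Section 1.3.1 names fetal harm as a possible risk on the basis of animal data. Section 4.1 (criterion 8d) says that a woman who could become pregnant "must agree to use a highly effective method of contraception during the study and for 3 months after the last study drug administration". Criterion 9 sets the same 3 months for men, covering birth control and sperm donation. Section 4.2 (criterion 2) excludes anyone planning a pregnancy or planning to father a child within that period, and Section 4.3.2.1 uses the same period in its stopping criteria. Live vaccines are "prohibited during the study and within 12 weeks after the last study drug administration" (Section 5.6.5; also Section 4.2, criterion 12).

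**End of observation.** Adverse events are assessed "through 6 weeks after the last dose of study drug" (Section 6.4.4). "The SFU visit is to be conducted 6 weeks after the last dose of study drug" (Section 6.1.8). Section 4.3.1 gives the same 6 weeks of safety follow-up to subjects who decline the long-term extension (LTE). Section 6.3 says a pregnancy test "must be performed 6 weeks after the last study drug administration", and Table 5 places it at the safety follow-up (SFU) visit.

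**Pregnancy reporting.** Section 6.4.7 says "any pregnancy that occurs during study participation (including pregnancy in a female partner of a male subject) must be reported". Reported pregnancies are followed to outcome, even after the subject has left the study.

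**Pregnancy testing.** Section 6.6.6 says the test "should be performed prior to receiving the first administration of study drug and as needed during the study". It gives the purpose as keeping an embryo or fetus from being exposed to study drug.

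**The concern.** The protocol asks subjects to avoid conception for 3 months and live vaccines for 12 weeks after the last dose. For a subject who leaves at the 6-week visit, nobody is scheduled to ask about either in the second half of those periods. Safety is the trial's secondary objective (Section 2.2). A pregnancy in a subject or partner conceived after that visit, but inside the period the protocol itself restricts, could be absent from the record unless someone volunteers it. Because only certain bad outcomes remain reportable later, such outcomes could be known without the number of pregnancies they came from.

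The testing text adds two smaller problems. Section 6.6.6 leaves out the 6-week test that Section 6.3, footnote j and Table 5 require. Its stated purpose also sits uneasily with Tables 2 and 3, which schedule no test between run-in (RI) baseline and the end-of-randomized-withdrawal (EORW) visit.

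**Working it through.** The protocol gives no figure for this point, so there is none to reproduce. The check is the share of each restriction period left after the last scheduled contact.

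**Inputs**
- Last scheduled contact: 6 weeks = 42 days after the last dose (Sections 6.1.8 and 4.3.1; Table 5, visit window ±2 days).
- Live-vaccine period: 12 weeks = 84 days (Section 5.6.5).
- Conception period: 3 months (Sections 4.1, 4.2 and 4.3.2.1). Assumption: 89 to 92 days, with 91 days (13 weeks) as the central value.

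**Formula:** share without contact = (period − 42) / period.

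- Live vaccines: (84 − 42) / 84 = 50.0%, or 6 of 12 weeks.
- Conception: (91 − 42) / 91 = 53.8%, or 7 of 13 weeks. At 89 days it is 47 / 89 = 52.8%; at 92 days it is 50 / 92 = 54.3%.
- With the visit held 2 days late or early (day 44 or 40): live vaccines 40 / 84 = 47.6% to 44 / 84 = 52.4%; conception 45 / 89 = 50.6% to 52 / 92 = 56.5%.

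**Does Section 6.4.7 close the gap?** Take a conception 8 weeks after the last dose, in a subject whose participation ended at the 6-week visit.
- The main reporting rule is tied to study participation, which has ended, so it does not apply.
- Pregnancy-associated SAEs that surface after completion are reportable, but only if they reach the investigator and are judged possibly related.
- Perinatal death or congenital abnormality is reportable with no time limit, but again only if it reaches the investigator.
- Follow-up to outcome presupposes that the pregnancy has been reported.

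An uncomplicated pregnancy therefore triggers no required report.

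**Live vaccine at week 9.** It is prohibited. Concomitant medications are last reviewed at the SFU visit (Table 5), so no scheduled contact would find it.

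**Pregnancy testing.** Table 2 marks screening and RI baseline, and Table 3 marks EORW only. Table 4 marks LTE Week 24 and the 18-month assessment, and Table 5 marks the SFU visit. Section 6.6.6 mentions only the test before the first dose and tests as needed.

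**The case against.** The strongest reply has four parts.

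1. **Section 6.4.4 does not govern pregnancy.** It limits adverse event collection, and Section 6.4.7 treats pregnancy as an adverse event only where interference with contraception is suspected. This stands. A reader might infer from the 6-week limit that pregnancy capture stops there. The text does not support that: Section 6.4.7 has no 6-week limit, and what stops at 6 weeks is scheduled contact.

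2. **Six weeks is not the last contact for everyone.** Subjects who stop drug early without withdrawing consent are followed through EORW, for the study period or for the trial (Sections 4.3.2, 6.1 and 6.1.8). RI non-responders are followed to the end of the randomized-withdrawal period (Section 3.1.2), and LTE subjects may remain under observation off treatment (Section 3.1.4). This also stands, and it confines the point to subjects whose participation ends at the SFU visit.

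3. **A restriction may outlast follow-up without contradiction.** That is correct. The 3-month and 12-week periods are eligibility and conduct rules, and the protocol never calls them observation periods. This is a gap in data collection, not an inconsistency between the windows.

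4. **Section 6.4.7 also covers a subject found pregnant after at least one dose, with no end date.** The sentence goes on to require that drug be stopped, so it most naturally addresses subjects still being treated. It does not mention partners, and it provides no contact through which a later pregnancy would be found.

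On testing during the randomized-withdrawal period, a reader might infer that subjects go 36 weeks to 2 years with undetected exposure. The documents do not support that. Tests are allowed as needed, half of the randomized subjects are assigned placebo, and the 36-week to 2-year range is the projected rilonacept dosing for subjects completing that period, not an interval between tests. Likewise, the omission in Section 6.6.6 is editorial, because the 6-week test is mandatory elsewhere.

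**Conclusion.** The point holds in a limited form. For subjects whose participation ends at the 6-week visit (those declining the LTE and those finishing it on treatment), about 54% of the 3-month conception period (52.8% to 54.3% depending on the length of the months, or 50.6% to 56.5% allowing for the visit window) and 50% of the 12-week live-vaccine period have no scheduled contact. Within that gap, an uncomplicated pregnancy in a subject or partner need not be reported.

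These are shares of time. The protocol gives no basis for estimating how many pregnancies or vaccinations would fall there, and no such estimate is made. The conclusion takes the protocol's restriction periods as given; whether they are clinically right is not judged here. It bears on the completeness of the safety record and not on the efficacy analyses.

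**What to change.** 1. Reconcile Section 6.4.7, and the follow-up in Sections 6.1.8 and 4.3.1, with the protocol's own post-dose restriction periods. Pregnancies in subjects or partners conceived within the stated contraception period should be reportable and followed to outcome, whether or not participation has ended.
2. Add one telephone contact at the end of that period, asking about pregnancy and live-vaccine exposure. One call covers both, since 84 days ends before 3 months (89 to 92 days).
3. Align Section 6.6.6 with Section 6.3, footnote j and Table 5 on the 6-week test.
4. Have the sponsor reconcile the purpose of testing stated in Section 6.6.6 with Tables 2 and 3, which schedule no test between RI baseline and EORW. No testing frequency is proposed here.

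The cost is amendment wording and one short call per affected subject. No dose, treatment or stopping rule changes.
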